1.3 Schedule of Activities

Once informed consent has been obtained, eDiary provision and training for site and home visits should occur first during SV1, followed by patient reported outcome (PRO) assessments. PRO assessments should be conducted first at all other visits. For all participants, in-clinic spirometry testing must be initiated between 6:00 AM and 11:00 AM during the screening or re-screening period, and randomisation visit (SV4). Whenever electrocardiograms (ECGs), vital signs, and blood draws are scheduled for the same nominal time, the order should be as follows: ECG, vital signs (vital signs can occur immediately after ECG using the same rest period), then blood draws. The timing of the first 2 assessments should be such that it allows the blood draw (eg, PK blood sample) to occur at the assigned nominal time. Whenever FeNO, airwave oscillometry (AO), and spirometry are scheduled for the same nominal time, the order should be as follows: FeNO, AO, then spirometry. Nasal sampling should be performed last, with nasal lining fluid collection performed before nasal epithelium collection (when both are scheduled). Urine samples may be collected at any time during the study visit (when scheduled). On days when investigational product is administered, all assessments should be performed pre-dose unless otherwise specified in the Schedule of Activities. Refer to Section 8 for additional information on assessment ordering (eg, pre-, post-dose or multiple timepoints within a visit). In the event that a clinical laboratory test result is not available from central laboratories during the screening period, see Section 8.2.7.

Table 1 Schedule of Activities: Screening Period

Visit Number	SV1	SV2	SV3
Procedure/Study Day	-35 to -28	-14 to -6	Visit no longer needed
Study Week	-4	-1	
Written ICF CCI /assignment of SID number	X ^a		
Written informed consent for future use and/or DNA analysis (optional)	X		
Verify eligibility criteria	X	X	
Demographics	X		
Baseline asthma assessments			
Provision of, and training on use of, home spirometry device and eDiary	X		
ACQ-6	X	X	
SGRQ		X	
SNOT-22 (comorbid CRS participants only)	X		
At-home eDiary completion and spirometry use	Twice daily throughout screening period		

Table 1 Schedule of Activities: Screening Period

Visit Number	SV1	SV2	SV3
Procedure/Study Day	-35 to -28	-14 to -6	Visit no longer needed
Study Week	-4	-1	
Assess adherence to at-home eDiary completion, spirometry, and SOC medication use		X	

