3.4.6 Asthma CompEx

Asthma CompEx is a combination of exacerbations of asthma and diary events (ie, combination of eDiary variables). Asthma CompEx is a composite surrogate endpoint for exacerbations of asthma, recently developed by AstraZeneca (it is not yet a regulatory-approved clinical endpoint).

Diary events are defined by the threshold and slope criteria using the following morning/evening (AM/PM) diary variables:

- PEF (variable 1=V1= morning PEF; variable 2=V2= evening PEF).
- Symptom score (0 – 3) (variable 5=V5= morning symptom score; variable 6=V6= evening symptom score).
- Use of rescue medication (variable 3=V3= morning rescue medication usage; variable 4=V4= evening rescue medication usage).

A subject will be considered to have a CompEx event if the subject has one or both of the following:

- 1 An asthma exacerbation,
- 2 A diary event, which is defined as either the threshold criterion or the slope criterion (or both), as defined below, being met for ≥ 2 consecutive days.

For this purpose, “2 consecutive days” means strictly the same 2 consecutive days when assessing multiple requirements within those days. For the eDiary data (which is captured twice during the day), one day will be defined by the morning/evening pairing for consistency with published precedent for the CompEx endpoint. (Note: other eDiary endpoints in this trial will use an evening/morning pairing to define one day.) The morning eDiary recordings captured on the first day of treatment will not be included in the calculation of the CompEx endpoint.

Threshold criterion:

- (a) $\geq 15\%$ decrease from baseline in either morning (V1) or evening home-based PEF (V2),
and at least one of the following:
- (b) ≥ 1.5 doses increase from baseline in rescue medication in either the morning (for preceding night, V3) or evening (for preceding day, V4),
- (c) ≥ 1 score increase from baseline, or the absolute maximal symptom score, in either the morning (V5) or evening (V6).

For (b), the number of doses of rescue medication is defined as the number of puffs of inhaler recorded in the morning and evening, respectively.

For (c), the asthma symptom score (scored 0-3) as described in Section 3.6.2.1 (V1-V6), provided those non-missing values meet the criterion.

Slope criterion:

One of (a), (b) or (c) above is met for ≥ 2 consecutive days *and* the regression slope requirement over the preceding 5 days is also met.

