The regression slope requirement in the preceding 5 days is that all of the following are met:

- Morning PEF slope $\leq -3\%/day$;
- Evening PEF slope $\leq -3\%/day$;
- Morning (preceding night) rescue medication slope ≥ 0.3 doses/day;
- Evening (preceding day) rescue medication slope ≥ 0.3 doses/day;
- Morning asthma symptom score slope ≥ 0.2 score/day;
- Evening asthma symptom score slope ≥ 0.2 score/day.

In all of the above cases, the regression slope is the point estimate of the slope obtained from a linear regression of the absolute values of each of the six variables (V1-V6) separately against day number, with no other variables included in the regression model.

For morning and evening PEF, the regression slope thus obtained will first also be divided by the baseline PEF value before applying the above criterion. The following table shows how the timing for the 5-day requirement for the regression slopes fits with the 2-consecutive day requirement, where “Day 0” here refers to the first of the 2 consecutive days (shaded) to be used each time the rolling 2 consecutive day assessment is made:

Table 3 Timing for assessment of CompEx slope criterion

	Day -4	Day -3	Day -2	Day -1	Day 0	Day 1
Threshold (a), (b), (c)					x	x
Slope	x	x	x	x	x	x

A regression slope will be calculated provided there are at least two non-missing values in the required 5 days. If one or more of the six variables above (V1-V6) does not have at least two non-missing values in the required 5 days, then the slope requirement therefore cannot be met.

The start date of a CompEx event is defined as the earliest of the exacerbation or objective deterioration start dates which meets the definition. Diary event start date is defined as the earliest Day 0 (in notation from Table 15) from any series of rolling 2 consecutive days which first qualifies using either the threshold or slope criterion.

The end date of a CompEx event is defined as the latest of the exacerbation or objective deterioration end dates which meets the definition. Diary event end date is defined as the latest Day 1 (in notation from Table 3 – Timing for assessment of CompEx slope criterion) from any series of rolling 2 consecutive days which last qualifies using either the threshold or slope criterion.

The event duration is defined as the end date minus the start date plus 1.

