If the end date of the first CompEx event and the start date of the second CompEx event are less than 7 days apart for any subject, then these will be counted as one CompEx event.

For CompEx analyses, only on-treatment events (based on the period from baseline to last dose date +28 days) will be considered. A supplementary analysis including events in the period from baseline to end of follow-up (Week 24) will also be conducted.

Time-to-first event will be defined as: [Start date of first event or censoring – date of 1st dose] + 1.

Date of first event will be the first start date of a CompEx event as defined above. For participants who do not experience an on-treatment CompEx event, date of censoring will be the minimum between the date of last dose plus 28 days, and the last day of eDiary recording during the on-treatment period. For the analysis of CompEx during combined treatment and follow-up period, date of censoring will be the minimum between the date of end of study visit, and the last day of eDiary recording during combined treatment and follow-up period .

For recurrent events, there must be a gap of 7 days between events ie, at least 7 days between end date of first CompEx event and start date of second CompEx event. Events that occur closer in time will be collapsed into one event.

The time during the event and the 7 days after each event will not be considered when defining time at risk for the CompEx event rate. Time at risk will be defined as [Date of last treatment plus 28 days– date of 1st dose] + 1 – recovery time. For the analysis of CompEx during combined treatment and follow-up period, the time at risk will be defined as [date of end of study visit – date of 1st dose] + 1 – recovery time.

The annualised rate of asthma CompEx events, during intervention period (Baseline to last dose date +28 days) per participant will be calculated as:

Annualised rate of asthma CompEx events during intervention period =

Total number of asthma CompEx events

$$\frac{\text{Total number of asthma CompEx events}}{(\text{Date of last dose of IP} + 28 - \text{Date of the first dose of IP} - \text{recovery time} + 1)/365.25}$$

where the recovery time is defined as:

$$\sum_{i=1}^k [\min(i^{\text{th}} \text{ event end date} + 7, \text{date of last dose} + 28) - i^{\text{th}} \text{ event start date} + 1]$$

The annualised rate of asthma CompEx events, during intervention and follow-up periods (Baseline to Week 24) per participant will be calculated as:

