
$$\text{Annualised rate of asthma CompEx events during intervention and follow-up periods} = \frac{\text{Total number of asthma CompEx events}}{(\text{Date of last follow up} - \text{Date of the first dose of IP} - \text{recovery time} + 1)/365.25}$$

Where the recovery time is defined as:

$$\sum_{i=1}^k [\min(i^{\text{th}} \text{ event end date} + 7, \text{date of last follow up}) - i^{\text{th}} \text{ event start date} + 1]$$

Rolling windows of time:

The deterioration criteria for the individual diary variables are defined as a combination of threshold criteria and regression slope criteria during each rolling window. Each rolling window contains 6 consecutive days, including 2 consecutive days for threshold assessment (Window Day 0 and 1), and 5 preceding consecutive days for regression slope assessment (Window Day -4 to 0). For this purpose, “2 consecutive days” means the same 2 consecutive days when assessing multiple threshold requirements. Similarly, ‘5 preceding consecutive days’ means the same 5 preceding consecutive days when assessing multiple slope requirements.

Rolling Window	Study Day	1	2	3	4	5	6	7	8	n	n+1	n+2	n+3	n+4	n+5
1	Window Day	-4	-3	-2	-1	0	1									
	Threshold Assessment					x	x									
	Slope Assessment	x	x	x	x	x										
2	Window Day		-4	-3	-2	-1	0	1								

Rolling Window	Study Day	1	2	3	4	5	6	7	8	n	n+1	n+2	n+3	n+4	n+5
	Threshold Assessment						x	x								
	Slope Assessment		x	x	x	x	x									
3	Window Day			-	-	-	-	0	1							
	Threshold Assessment			4	3	2	1			x	x					
	Slope Assessment		x	x	x	x	x									
.....																
n	Window Day									-	-3	-2	-1	0	1	
	Threshold Assessment													x	x	
	Slope Assessment									x	x	x	x	x		

The deterioration criteria are assessed for a series of rolling windows over the entire study duration. For example, Window 1 includes ‘Study Day 1’ through ‘Study Day 6’, Window 2 rolls one day forward that includes ‘Study Day 2’ through ‘Study Day 7’, Window 3 rolls one day forward that includes ‘Study Day 3’ through ‘Study Day 8’, and so on so forth, as illustrated in the table below:

Table 46 Rolling windows of time

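### SAP 3.4.6 defines the CompEx threshold criterion on any 2 consecutive days, but its rolling windows first test it on Study Days 5 and 6

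*SAP*

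**What the plan says.** SAP 3.4.6 describes the diary component of CompEx twice.

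The definition comes first. A CompEx event is an asthma exacerbation, a diary event, or both. The second is "A diary event, which is defined as either the threshold criterion or the slope criterion (or both), as defined below", the chosen criterion "being met for ≥ 2 consecutive days". The threshold criterion compares PEF, rescue use and symptom score with baseline, and needs no earlier on-treatment days. The only early diary data set aside are the Day 1 morning entries. "Diary event start date is defined as the earliest Day 0" among the runs of 2 consecutive days that qualify.

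The subsection on rolling windows follows. "Each rolling window contains 6 consecutive days, including 2 consecutive days for threshold assessment (Window Day 0 and 1"; window days -4 to 0 serve the slope. It adds that "The deterioration criteria are assessed for a series of rolling windows over the entire study duration". In the worked example, "Window 1 includes ‘Study Day 1’ through ‘Study Day 6", and the rolling-window table marks the threshold test for that window on Study Days 5 and 6.

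The clock is set separately. "Time at risk will be defined as [Date of last treatment plus 28 days" minus the first-dose date, plus 1, less recovery time. Time to first event is also counted from the first dose.

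**The concern.** The two descriptions select different events. Under the definition, a participant who meets the threshold on Days 2 and 3 has a diary event. Under the rolling-window text that pair is never tested. Two programmers, each faithful to one part of the same section, could produce different event lists, start dates and recovery times.

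Time to first CompEx event and the annualised CompEx rate are both secondary endpoints (SAP Table 1, Objectives and Endpoints), so their derivation should be reproducible from the text. The SAP gives no reason for a lead-in on the threshold criterion. Its amendment history describes the rolling-window text as a clarification, so a programmer could reasonably treat that text as the operative rule.

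**Working it through.** **Inputs**
- Window of 6 days, labelled -4 to 1, with the threshold on window days 0 and 1; Window 1 is Study Days 1 to 6 (SAP 3.4.6).
- Diary-event start is the earliest qualifying window day 0 (SAP 3.4.6).
- Time at risk = (last dose + 28 - first dose) + 1 - recovery time (SAP 3.4.6).
- Recovery time per event = (event end + 7) - event start + 1, when not cut off by the end of the period (SAP 3.4.6).
- Last scheduled dosing visit is SV9, Study Day 85 (SAP 3.5.2 with Protocol Table 2).

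**First pair tested.** Window k covers Study Days k to k+5, so window day 0 is k+4 and window day 1 is k+5.
- k = 1 gives Days 5 and 6, which matches the SAP's example and table.
- k = 2 gives Days 6 and 7.
- The earliest possible diary-event start is therefore Study Day 5.

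**Pairs missed with scheduled dosing.**
- Time at risk with no events = (85 + 28 - 1) + 1 = 113 days.
- Days 1 to 113 contain 112 consecutive-day pairs.
- The windows test the pairs from (5,6) to (112,113), which is 108.
- 112 - 108 = 4 are never tested: (1,2), (2,3), (3,4) and (4,5).

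**Share of days at risk that cannot hold a diary-event start** (no events, first dose Day 1):

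| Last dose or period | Days at risk | Share |
|---|---|---|
| Day 85 | 113 | 4/113 = 3.5% |
| Day 57 | 85 | 4/85 = 4.7% |
| Day 29 | 57 | 4/57 = 7.0% |
| Day 1 | 29 | 4/29 = 13.8% |
| Supplementary analysis to Week 24 | 169 | 4/169 = 2.4% |

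**Two illustrative participants**
- Threshold met on Days 2 and 3 only. Definition: one event, starting Day 2. Rolling windows: no event.
- Threshold met on Days 2 to 6. Definition: start Day 2, time to event 2 days, recovery time (6 + 7) - 2 + 1 = 12 days. Rolling windows: start Day 5, time to event 5 days, recovery time (6 + 7) - 5 + 1 = 9 days. Days 2 to 4, which belong to the event, stay in time at risk.

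**The case against.** The best reply is that the section is ambiguous and does not settle on a blind period. The definition has no lead-in. The 6-day timing grid that follows it is titled for the slope criterion. The Study Day numbers are introduced as an example, and the windows are said to span the whole study. A programmer could read all this as allowing threshold pairs from Day 1 or 2. That is fair, and it is why the point is a contradiction to be resolved. It does not remove the problem: the rolling-window text names the threshold test explicitly, and its table agrees with its example.

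Four stronger readings are tempting, and the documents do not support them.
- *Days 1 to 4 should not be time at risk.* An asthma exacerbation on those days is a CompEx event, so starting the clock at first dose is right for that component.
- *About 3.5% of diary events are lost.* That figure is a share of days. A deterioration still present on Days 5 and 6 is kept and only dated late. How many resolve earlier, and whether events are evenly spread, is not in the documents. Day 1 also offers only an evening entry.
- *The treatment comparison is biased.* The rule is identical in all arms, so nothing points to a material effect on rate or hazard ratios.
- *The early slopes must use pre-dose data, because the diary is kept* "Twice daily throughout screening period". Availability does not make this a correction. Pre-dose decline could then help trigger an event counted as on-treatment, those days already form part of the 14-day CompEx baseline, and the study-day numbering in SAP 3.1.2 has no Day 0. Starting slopes at Day 1 is defensible.

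**Conclusion.** The contradiction is real and its effect is small. Read literally, the rolling-window rule prevents any diary event from starting before Study Day 5, whereas the definition allows a start from Day 1 (evening entry) or Day 2. Threshold-only deteriorations that are over before the Day 5 and 6 test are missed; those that persist are dated from Day 5. The affected share is 3.5% of days at risk with scheduled dosing, and up to 13.8% for a participant who receives only the Day 1 dose.

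These shares assume dosing on scheduled days and no recovery time. What is at stake is the event count, start dates, recovery time, absolute rates and the first days of the Kaplan-Meier curve. The between-arm ratios should be little affected.

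**What to change.** In SAP 3.4.6:
- State that the 6-day window governs the slope criterion only.
- Test the threshold criterion on every consecutive-day pair, beginning with Study Day 1 (evening entry) and Day 2.
- Correct the Window 1 example and the rolling-window table to match.

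The slope criterion may remain first assessable at Window 1, as now written. Using pre-dose diary days for it is optional and would need its own rationale and day numbering. If a lead-in for the threshold criterion was intended, the SAP should say so, justify it and state how diary-event time at risk is handled.

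The cost is a few lines of SAP text, one table and a small programming change. No new data are needed.

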3.4.7 Fractional Exhaled Nitric Oxide (FeNO)

Percent change from baseline to Week 16 in concentration of FeNO in exhaled breath is a secondary endpoint of this study. Additionally, percent and relative change from baseline to Weeks 1, 4, 8, 12, 16, 20, and 24 will be analysed as exploratory endpoints.

Airway inflammation will be evaluated using a standardised single-breath FeNO test at visits SV1, SV2, SV4, SV6, SV7, SV8, SV9, SV10, SV11, SV12 and E/D. Two acceptable FeNO measurements will be performed to establish repeatability; up to 8 measurements can be performed. The mean value of the measurements, as provided by the vendor, will be used in the statistical analysis. Percent and relative change from baseline in FeNO will be derived in accordance with Section 3.1.3 of this SAP.

3.5 Derivation of safety variables

3.5.1 Adverse events (AEs)

AEs will be collected from signing of ICF throughout the intervention period and including the follow-up period. SAEs will be recorded from the time of signing of ICF. AEs will be coded with MedDRA version 25.0 or higher.

AE data will be allocated to the study phase (as defined in section 3.1.4) according to their onset date. AEs will be defined as treatment emergent adverse events (TEAEs) if they have an onset during the on-treatment phase. AEs with a missing start date will be considered as on-treatment.

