8.3.1 Time Period and Frequency for Collecting AE and SAE Information

Adverse events will be collected from signing of ICF throughout the treatment period and including the follow-up period. SAEs will be recorded from the time of signing of ICF.

If the investigator becomes aware of an SAE with a suspected causal relationship to the study intervention that occurs after the end of the clinical study in a participant treated by him or her, the investigator shall report the SAE to the sponsor within 24 hours.

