8.3.2 Follow-up of AEs and SAEs

Any AEs that are unresolved at SV12 in the study are followed up by the investigator for as long as medically indicated, but without further recording in the eCRF. AstraZeneca retains the right to request additional information for any participant with ongoing AE(s)/SAE(s) at the end of the study, if judged necessary.

Adverse event variables

The following variables will be collected for each AE:

- AE (verbatim).
- The date and time when the AE started and stopped.
- Severity grade.
- Whether the AE is serious or not.
- Investigator causality rating against the study intervention (yes or no).
- Action taken with regard to study intervention.

- AE caused participant’s withdrawal from study (yes or no).
- Outcome.

In addition, the following variables will be collected for SAEs:

- Date AE met criteria for serious AE.
- Date investigator became aware of serious AE.
- AE is serious due to.
- Date of hospitalisation.
- Date of discharge.
- Probable cause of death.
- Date of death.
- Autopsy performed.
- Causality assessment in relation to study procedure(s).
- Causality assessment to other medication.

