Period 4: Evening of Day 43 – Morning of Day 57	Week 8	57
Period 5: Evening of Day 57 – Morning of Day 71	Week 10	71
Period 6: Evening of Day 71 – Morning of Day 85	Week 12	85
Period 7: Evening of Day 85 – Morning of Day 99	Week 14	99
Period 8: Evening of Day 99 – Morning of Day 113	Week 16	113
Period 9: Evening of Day 113 – Morning of Day 127	Week 18	127
Period 10: Evening of Day 127 – Morning of Day 141	Week 20	141
Period 11: Evening of Day 141 – Morning of Day 155	Week 22	155
Period 12: Evening of Day 155 – Morning of Day 169	Week 24	169

The Early Discontinuation and unscheduled visits will be included when applying the visit windows to ensure that all available data are used in the analysis.

For bi-weekly summaries, the mean of all non-missing observations within an assigned window is calculated. If there are fewer than 10 completed days in the 14 day period (where a

complete day = entry from the evening AND the following morning) then the analysis value will be set to missing.

Finally, for the purpose of the statistical analysis, the assessments will be allocated to the study phase in which they are collected as reported below.

Table 2 Study phase windows

Study phase	Phase Window for Analysis (Days)
Pre-treatment	Prior to the first administration of investigational product (day <1 ^a)
On-treatment	≥ day 1 ^b to last dose date plus 28 days (included)
Follow-up	> last dose date plus 28 days

^a Includes all measurements collected before first dose of IP. If the measurement is collected on day 1 it cannot be determined if it was done before or after the first dose of IP (due to missing time and/or planned time point), then it will be considered as collected after first dose of IP.

^b Includes all measurements collected on the day of first dose of IP, at the time of IP intake and after.

Unless otherwise specified, the study phase will be mainly used for safety analysis (e.g., laboratories, adverse events) and for CompEx analysis.

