4.2.7.1 Analysis of AEs

All AE summary tables and listings will be created by treatment group and for total MEDI3506 for the As-treated population, unless otherwise specified. AEs occurred during study intervention (on-treatment phase as defined in section 3.1.4) and follow-up period (follow-up phase as defined in section 3.1.4) will be reported in summary tables. All AEs, including AEs for enrolled but not randomised participants and for participants who were not exposed to treatment, will be listed.

An overall summary table will be produced by treatment group and for total MEDI3506 showing the number and percentage of participants with at least one AE in any of the following categories:

- AEs;
- AEs with toxicity grade 4 or 5;
- Serious adverse events (SAEs);

- Deaths due to AE;
- AEs leading to discontinuation of IP;
- AEs leading to dose interruption;
- AEs leading to withdrawal from study;
- AESI.

The total number of AEs in the different AE categories in terms of AE counts (ie, accounting for multiple occurrences of the same event in a subject) will also be presented by treatment group and for total MEDI3506.

Number and percentage of participants with at least one AE by SOC term will be produced by treatment group and for total MEDI3506.

Number and percentage of participants with at least one AE by PT will be produced for AEs with a frequency of > 5% by treatment group and for total MEDI3506. Frequency will be defined according to percentage in total MEDI3506.

Number and percentage of participants with AE by SOC and PT will be summarised by treatment group and for total MEDI3506.

Number and percentage of participants with AE by PT and maximum reported toxicity grade will be summarised by treatment group and for total MEDI3506 in table and AEs with frequency of >5% per treatment group will be graphically displayed using bar graphs. Each participant is represented only for the maximum reported intensity of each PT. Frequency will be defined according to percentage in total MEDI3506.

Number and percentage of participants with AEs by PT and investigator's causality assessment will be summarised by treatment group and for total MEDI3506.

Total number of AEs by SOC and PT will be summarised by treatment group and for total MEDI3506. Total number of SAEs by SOC and PT will be summarised by treatment group and for total MEDI3506.

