Number and percentage of participants with AE leading to dose interruption by SOC and PT will be summarised by treatment group and for total MEDI3506.

Number and percentage of participants with non-serious AEs and number of non-serious events occurring in more than 5% of participants will be summarised by SOC and PT.

Number and percentage of participants with AE with outcome of death by SOC and PT will be summarised by treatment group and for total MEDI3506. Key subject information for

participants experience AEs with outcome of death will be produced for each treatment group using following information:

- Treatment group
- Subject identifier
- Sex
- Age (years)
- Event term as reported by the investigator
- PT
- Time from first IP administration to onset of AE (days) as derived in Section 3.1.6.6
- Treatment period
- Time from last IP administration to death (days) as derived in Section 3.1.6.9
- Time from first IP administration to death (days) as derived in Section 3.1.6.8
- Received treatment for AE
- Reasonable possibility AE caused by IP

Number and percentage of participants with SAE by SOC and PT will be summarised by treatment group and for total MEDI3506. Key subject information for participants experience SAEs will be produced using following information:

- Treatment group
- Subject identifier
- Sex
- Age (years)
- Event term as reported by the investigator
- PT
- Time from first IP administration to onset of AE (days) as derived in Section 3.1.6.6
- Time from last IP administration prior to AE start date, calculated for AEs starting after the discontinuation of the IP.
- Time from start of IP administration to becoming serious
- Outcome
- Action taken with IP
- Reasonable possibility AE caused by IP.

Number and percentage of participants with AE leading to discontinuation of IP by SOC and PT will be summarised by treatment group and for total MEDI3506. Key subject information for participants experience AEs leading to discontinuation of IP will be produced using following information:

- Treatment group
- Subject identifier
- Sex
- Age
- AE as reported by the investigator
- PT
- Time from first IP administration to AE onset
- Time from first IP administration to discontinuation of IP
- Seriousness
- Outcome
- Reasonable possibility AE caused by IP.

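### Because the SAP sorts AEs by onset date alone, an AE that starts in screening and becomes serious after first dose is listed but missing from the by-arm safety tables

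*SAP*

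**What the plan says.** **Collection.** Protocol 8.3.1: "Adverse events will be collected from signing of ICF throughout the treatment period and including the follow-up period". For each AE, Protocol 8.3.2 records start and stop, a severity grade and whether it is serious. For SAEs it adds "Date AE met criteria for serious AE" as a separate variable. It lists no date of a change in grade.

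**Phases.** In SAP 3.1.4 the pre-treatment phase is "Prior to the first administration of investigational product". The on-treatment phase runs from Day 1 to last dose plus 28 days, and follow-up is everything later.

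**Allocation.** SAP 3.5.1: "AE data will be allocated to the study phase (as defined in section 3.1.4) according to their onset date", and "AEs will be defined as treatment emergent adverse events (TEAEs) if they have an onset during the on-treatment phase". The only exception there is that "AEs with a missing start date will be considered as on-treatment".

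**Tabulation.** SAP 4.2.7.1 selects for the summary tables "AEs occurred during study intervention (on-treatment phase as defined in section 3.1.4) and follow-up period", the latter meaning the follow-up phase. All AEs are listed. The section gives no separate selection rule for the SAE, death, discontinuation, AESI or toxicity-grade tables. Among the items shown for each SAE is "Time from start of IP administration to becoming serious".

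Protocol 9.4.4 does not define a TEAE, and SAP Section 6 does not mention the matter.

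**The concern.** The protocol's safety endpoint (Section 3, Table 4) covers AEs, SAEs and AESIs in the intervention and follow-up periods. An event that first meets serious criteria on, say, Day 30 becomes an SAE in the intervention period. If it began in screening, the onset rule leaves it in the pre-treatment phase, and the SAE table for its arm omits it.

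The effect reaches the tables read first. Under Protocol 7.1, a cardiac SAE or any SAE of Grade 4 or above ends dosing. A screening-onset event that turned into one would stop treatment, yet be absent from the table of AEs leading to discontinuation. A fatal one would be absent from the death table.

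The rule also sits oddly with the SAP's caution elsewhere. An AE with no start date counts as on-treatment (3.5.1), and a missing causality is taken as related (3.1.5). A fully dated screening AE that turns serious on study is thus treated less conservatively than an undated one.

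**Working it through.** The point concerns a definition. No sample size, power or event count in the plan depends on it, so there is no figure to reproduce. The check applies the written rules to test cases.

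**Inputs**
- Phase, by onset day (SAP 3.1.4 and 3.5.1): before Day 1 is pre-treatment; Day 1 to last dose + 28 is on-treatment; later is follow-up; a missing onset is on-treatment.
- Tabulated (SAP 4.2.7.1): on-treatment or follow-up phase.
- Assumed last dose: Day 85, the scheduled day of SV9. The on-treatment phase then ends on Day 85 + 28 = Day 113. This choice does not affect how pre-dose onsets are classed by the current rule.

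**Current rule**

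| Case | Phase | In summary tables |
|---|---|---|
| Onset Day -10, serious on Day 30, same record | Pre-treatment | No |
| Onset Day -10, grade rises on Day 30, same record | Pre-treatment | No |
| Worsening entered as a new AE, onset Day 30 | On-treatment | Yes |
| Start date missing | On-treatment | Yes |
| Onset Day 150 | Follow-up (150 > 113) | Yes |

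The first two rows show the gap. The third shows that the worsening part depends on how the site records it. The seriousness part is firmer, because the seriousness date is an attribute of the same AE record.

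**Choice of remedy**

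One simple repair would assign every SAE to a phase by the later of its onset and seriousness dates. That goes wrong for an AE with onset on Day 100 that turns serious on Day 120. Because 120 > 113, it would move to follow-up although its onset was on treatment. Restricting the change to pre-dose onsets avoids this:

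| Case | Phase under the restricted rule |
|---|---|
| Onset Day -10, serious on Day 30 (1 ≤ 30 ≤ 113) | On-treatment, TEAE |
| Onset Day -10, serious on Day 130 (130 > 113) | Follow-up, tabulated |
| Onset Day 100, serious on Day 120 | On-treatment, unchanged |

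**The case against.** The best case on the other side has four parts.

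- **Sites may already enter a new record.** Protocol Appendix B 1 allows the worsening of an existing condition to be an AE. Protocol 8.3.6 asks for an AE when a physical-examination finding is new or worse than at baseline, and when certain laboratory or vital-sign values deteriorate. Protocol 8.3.4 does the same for clinically significant asthma worsening. A worsening so entered has a post-dose onset and is counted. This stands, and it makes the worsening part conditional. None of these sections, however, requires a new record for a screening AE that is still open, and the eCRF guidance is not among the documents.
- **The events are not lost.** All AEs are listed, and partial start dates in the month or year of first dose are imputed to first dose unless the event ended earlier (SAP 3.1.5.1). Laboratory, ECG, LVEF and NT-proBNP results are summarised from measured values whatever the AE onset, and exacerbations have their own analysis. This stands too. A listing, however, does not give a count by arm.
- **Separate seriousness dates prove little.** A reader might infer from them that both documents expect screening events to turn serious on drug. They serve equally for an AE that starts after dosing and turns serious later, so that inference is not supported. The dates show only that the information needed for a fix is collected.
- **Few events may be at issue.** Exclusion criteria 13 to 15 apply through randomisation and keep out many active conditions. This also stands.

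**Conclusion.** The gap is real but limited. For an AE with pre-dose onset that becomes serious after first dose on the same record, the written rule gives a wrong count in the by-arm AE, SAE, AESI, discontinuation, death and maximum-grade tables. For an AE that only worsens, this holds if the original record and start date are kept.

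A reader might conclude that every screening AE that worsens on study disappears from the tables. The documents do not support that, because a worsening entered as a new AE is counted.

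The size cannot be computed from the documents. A reader might assume that 10–20% of 228 participants have a screening AE ongoing at Day 1 (0.10 × 228 ≈ 23 to 0.20 × 228 ≈ 46), and that 5–10% of these worsen or turn serious. That gives about 1 to 5 participants (0.05 × 23 ≈ 1; 0.10 × 46 ≈ 5). Neither rate is in either document, and the total mixes worsening with seriousness across all three arms. It therefore does not show that a comparison of SAEs between arms would change. The number is unknown and probably small. The correction is still worth making, because the events concerned are serious ones and the seriousness part needs no new data.

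**What to change.** **Seriousness, in SAP 3.5.1.** Also define as a TEAE any AE with onset before first dose that first meets serious criteria between first dose and last dose plus 28 days, using the seriousness date already collected. Allocate it to the on-treatment phase, because SAP 4.2.7.1 selects by phase. If it first meets serious criteria after that, allocate it to the follow-up phase so that it is tabulated. Apply both rules only to pre-dose onsets, so that AEs with on-treatment onset keep their phase.

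**Worsening.** Treat an increase in grade after first dose as treatment-emergent, and instruct sites to record it as a new AE dated at the worsening. The instruction is needed because no grade-change date is collected. The original record stays pre-treatment, so that the episode is not counted twice in the event-count tables.

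**Cost.** A few lines of SAP text, one programming rule for the seriousness part, and one line of eCRF guidance for the worsening part. Slightly more TEAEs will be counted.
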